8.1. Efficacy Assessment

Not applicable.

8.2. Safety Assessments

Planned time points for all safety assessments are provided in the SoA Section [1.3](#).

8.2.1. Physical Examinations

- A complete physical examination will include, at a minimum, assessments of the skin, cardiovascular, respiratory, gastrointestinal and neurological systems. Height and weight will also be measured and recorded.
- A brief physical examination will include, at a minimum, assessments of the skin, lungs, cardiovascular system and abdomen (liver and spleen).
- Investigators should pay special attention to clinical signs related to previous serious illnesses.

8.2.2. Vital Signs

- Vital signs will be measured in a semi-supine position after 5 minutes rest and will include temperature, systolic and diastolic blood pressure, and pulse.

8.2.3. Electrocardiograms

- Triplicate 12-lead ECG will be obtained as outlined in the SoA (see Section 1.3) using an ECG machine that automatically calculates the heart rate and measures PR, QRS, QT, and QTc intervals. 12-lead ECGs will be performed with the subject in a supine/semi-supine position having rested in this position for at least 5 minutes beforehand. Refer to Section 7.1.2 for QTc withdrawal criteria and additional QTc readings that may be necessary.
- At each time point at which triplicate ECG are required, 3 individual ECG tracings should be obtained as closely as possible in succession, but no more than 2 minutes apart. The full set of triplicates should be completed in less than 6 minutes.

8.2.4. Clinical Safety Laboratory Assessments

- Refer to [Appendix 2](#) for the list of clinical laboratory tests to be performed and to the SoA for the timing and frequency.
- The investigator must review the laboratory report, document this review, and record any clinically relevant changes occurring during the study in the AE section of the CRF. The laboratory reports must be filed with the source documents. Clinically significant abnormal laboratory findings are those which are not associated with the underlying disease, unless judged by the investigator to be more severe than expected for the participant's condition.
- All laboratory tests with values considered clinically significantly abnormal during participation in the study should be repeated until the values return to normal or baseline or are no longer considered significantly abnormal by the investigator or medical monitor.
- If such values do not return to normal/baseline within a period of time judged reasonable by the investigator, the aetiology should be identified, and the sponsor notified.

- All protocol-required laboratory assessments, as defined in [Appendix 2](#), must be conducted in accordance with the laboratory manual and the SoA.
- **Screening for SARS-CoV-2:** Study participants will be monitored at Screening and daily while inpatients for COVID-19 symptoms. Investigator(s) should utilise the World Health Organization (WHO) Case Definitions to classify COVID-19 cases [[World Health Organization](#), 2020]. While outpatients, participants should report to the unit any symptoms suggestive of COVID-19. All participants who experience symptoms suggestive of COVID-19 should be isolated in the unit or at home and tested for SARS-CoV-2 using an approved molecular test (PCR) or an immunological test for a viral antigen. The investigator should consider any participant testing positive for SARS-CoV-2 being discontinued from study drug if COVID-19 symptoms are moderate to severe. Appropriate contact tracing for all participants testing positive will be performed within the unit. This should be done in accordance with local legislation and guidelines. Appropriate follow up should be implemented for participants who discontinue the study due to COVID-19.

8.2.5. Suicidal Ideation and Behaviour Risk Monitoring

Participants should be monitored appropriately and observed closely for suicidal ideation and behaviour or any other unusual changes in behaviour. It is recommended that the investigator consider mental health consultation or referral for participants who experience signs of suicidal ideation or behaviour. Participants presenting with new onset/treatment emergent depression should be advised to contact the investigator immediately if symptoms of severe acute depression (including suicidal ideation/attempts) develop, because medical intervention and discontinuation of the study medication may be required.

8.2.6. Assessment of Injection Site Reactions

Injection Site Reaction examination will include an assessment of pain (or tenderness), pruritis, warmth, infections, rash, erythema (or redness), swelling (or induration), and nodules (granulomas or cysts). Digital photographs will be documented on all participants who have an injection site reaction that are considered more serious by the principal investigator (PI), e.g. Grade 2 or above or if persistent beyond 2 weeks.

Injection site erythema/redness or swelling/induration will be evaluated and graded using the greatest measured surface area (as well as impact with usual social and functional activities) as per DAIDS and data regarding the size of these injection site reactions recorded at each ISR assessment. The greatest width and length of these injections site reactions should be recorded in the CRF at each ISR assessment (Cohorts 4, 5 and 6). If the grade of an ISR changes over time, each change will also be recorded in the CRF. See Section [11.7](#) The Division of AIDS Table for Grading the Severity of Adult and Pediatric Adverse Events (“DAIDS AE Grading Table”).

8.2.6.1. Diary Cards

Participants will complete a diary card following each injection. This allows participants to record and score the severity of any reactions as well as record any action taken such as use of analgesic medication prophylactically or following the injection. Participants will also be asked to collect their temperature daily for 14-days following each injection. Concomitant medication will be recorded in the CRF.

CCI

8.2.6.3.

CCI

CCI

8.2.6.4.

CCI

CCI

8.3. Adverse Events and Serious Adverse Events

The definitions of an AE or SAE can be found in [Appendix 3](#).

AEs will be reported by the participant (or, when appropriate, by a caregiver, surrogate, or the participant's legally authorized representative).

The investigator and any qualified designees are responsible for detecting, documenting, and reporting events that meet the definition of an AE or SAE and remain responsible for following up AEs that are serious, considered related to the study intervention or the study, or that caused the participant to discontinue the study intervention or study (see [Section 7](#)).

The method of recording, evaluating, and assessing causality of AEs and SAEs and the procedures for completing and transmitting SAE reports are provided in [Section 11.3](#).

8.3.1. Time Period and Frequency for Collecting AE and SAE Information

- All SAEs will be collected from the start of intervention until the follow-up visit at the time points specified in the SoA ([Section 1.3](#)). However, any SAEs assessed as related to study participation (e.g., study intervention, protocol-mandated procedures,

invasive tests, or change in existing therapy) or related to a GSK product will be recorded from the time a participant consents to participate in the study.

- All AEs will be collected from the start of intervention until the follow-up visit at the time points specified in the SoA (Section 1.3).
- Medical occurrences that begin before the start of study intervention but after obtaining informed consent will be recorded on the Medical History/Current Medical Conditions section of the CRF not the AE section.
- All SAEs will be recorded and reported to the sponsor or designee immediately and under no circumstance should this exceed 24 hours, as indicated in Appendix 3. The investigator will submit any updated SAE data to the sponsor within 24 hours of it being available.
- Investigators are not obligated to actively seek AEs or SAEs after the conclusion of the study participation. However, if the investigator learns of any SAE, including a death, at any time after a participant has been discharged from the study, and he/she considers the event to be reasonably related to the study intervention or study participation, the investigator must promptly notify the sponsor.

8.3.2. Method of Detecting AEs and SAEs

- The method of recording, evaluating, and assessing causality of AEs and SAEs and the procedures for completing and transmitting SAE reports are provided in Appendix 3.
- Care will be taken not to introduce bias when detecting AE and/or SAE. Open-ended and non-leading verbal questioning of the participant is the preferred method to inquire about AE occurrence.

8.3.3. Follow-up of AEs and SAEs

After the initial AE/SAE report, the investigator is required to proactively follow each participant at subsequent visits/contacts. All SAEs, non-serious AEs such as ISRs, will be followed until the event is resolved, stabilized, otherwise explained, or the participant is lost to follow-up (as defined in Section 7.3). Further information on follow-up procedures is given in Appendix 3.

8.3.4. Regulatory Reporting Requirements for SAEs

- Prompt notification by the investigator to the sponsor of a SAE is essential so that legal obligations and ethical responsibilities towards the safety of participants and the safety of a study intervention under clinical investigation are met.
- The sponsor has a legal responsibility to notify both the local regulatory authority and other regulatory agencies about the safety of a study intervention under clinical investigation. The sponsor will comply with country-specific regulatory requirements relating to safety reporting to the regulatory authority,

Institutional Review Boards (IRB)/Independent Ethics Committees (IEC), and investigators.

- For all studies except those utilizing medical devices investigator safety reports must be prepared for suspected unexpected serious adverse reactions (SUSAR) according to local regulatory requirements and sponsor policy and forwarded to investigators as necessary.
- An investigator who receives an investigator safety report describing a SAE or other specific safety information e.g., summary or listing of SAEs) from the sponsor will review and then file it along with the Investigator's Brochure and will notify the IRB/IEC, if appropriate according to local requirements.

8.3.5. Pregnancy

- Details of all pregnancies in female participants will be collected after the start of study intervention and until the last follow up visit.
- If a pregnancy is reported, the investigator should inform GSK within 24 hours of learning of the pregnancy and should follow the procedures outlined in [Appendix 4](#).
- If a participant should become pregnant during the oral lead-in phase, the study product will be immediately discontinued, and the participant will continue to be followed for safety evaluations every 4-5 weeks until the pregnancy outcome is reached, at which point the participants will be terminated from the study. If a participant should become pregnant at any time point after the IM CAB LA injection has been received, she will continue on study and will receive the appropriate safety follow-up evaluations per the SoA.
- Abnormal pregnancy outcomes (e.g., spontaneous abortion, fetal death, stillbirth, congenital anomalies, ectopic pregnancy) are considered SAEs.

8.4. Treatment of Overdose

For the oral lead in period of this study, any tablet intake exceeding a total daily dose of 30 mg will be considered an overdose.

For the injection phase of the study, any dose of CAB 400 mg/mL and CAB 200 mg/mL LA above those specified for each cohort in this protocol and/or selected by the STR for a cohort will be considered an overdose.

GSK/ViiV Healthcare does not recommend specific treatment other than supportive care for an overdose.

- The investigator will use clinical judgement to treat any overdose. Contact the Medical Monitor immediately.
- Closely monitor the participant for AE/SAE and laboratory abnormalities for 52 weeks following the last injection or until CAB can no longer be detected systemically.

- Obtain a plasma sample for PK analysis as soon as possible if requested by the Medical Monitor (determined on a case-by-case basis).
- Document the quantity of the excess dose as well as the duration of the overdosing.

Decisions regarding dose interruptions or modifications will be made by the investigator in consultation with the Medical Monitor based on the clinical evaluation of the participant.

8.5. Pharmacokinetics

Blood samples of approximately 2 mL will be collected for measurement of plasma concentrations of CAB as specified in the SoA.

- Samples may be collected at additional time points during the study if warranted and agreed upon between the investigator and the sponsor. The timing of sampling may be altered during the course of the study based on newly available data (e.g., to obtain data closer to the time of peak plasma concentrations) to ensure appropriate monitoring.
- Instructions for the collection and handling of biological samples will be provided by the sponsor. The actual date and time (24-hour clock time) of each sample will be recorded.
- Samples will be used to evaluate the PK of CAB. Genetic analyses will not be performed on these plasma samples.
- **Permitted sampling window for the OLI phase:**

Plasma PK Assessment	Permitted Sampling Window
Day 1 (1 h)	±15 min
Day 1 (2 h)	±15 min
Day 1 (3 h)	±15 min
Day 1 (4 h)	±15 min
Day 1 (6 h)	±30 min
Day 1 (8 h) (Cohorts 5 and 6 only)	±1 h
Day 1 (12 h) (Cohorts 5 and 6 only)	±1 h
Day 2 (24 h)	±4 h (i.e. 20-28 h from Day 1 dose)

Plasma PK Assessment	Permitted Sampling Window
Day 14	±1 day
Day 29	20-28 h from Day 28 dose

Permitted sampling window for the injection phase is provided in the SoA.

8.6. Pharmacodynamics

Pharmacodynamic parameters are not evaluated in this study.

8.7. Genetics

A 6 mL blood sample for DNA isolation will be collected from participants who have consented to participate in the genetics analysis component of the study. Participation is optional. Participants who do not wish to participate in the genetic research may still participate in the study.

In the event of DNA extraction failure, a replacement genetic blood sample may be requested from the participant. Signed informed consent will be required to obtain a replacement sample unless it was included in the original consent.

See [Appendix 5](#) for Information regarding genetic research. Details on processes for collection and shipment and destruction of these samples can be found in SRM.

8.8. Biomarkers

Biomarkers are not evaluated in this study.

8.9. Immunogenicity Assessments

Plasma samples will be collected for storage (pre-dose, Day 14 and Day 28). It is considered unlikely that recombinant human protein rHuPH20 induces an anti-drug antibody (ADA) response in healthy volunteers after a single dose, particularly at low doses. Immunogenicity analysis will be performed on these stored samples if there are safety events suggestive of immune-mediated reactions. Please refer to the SRM for additional instructions regarding storage and processing of these samples.

CCI

CCI

9. PHARMACOKINETIC METHOD OF ANALYSES

The department of Clinical Pharmacology Modelling & Simulation (CPMS) will be responsible for the PK analysis of data from Parts 1 and 2.

PK analysis of the plasma CAB concentration-time data will be conducted using non-compartmental methods with WinNonlin (Version 6.3 or higher). Actual sampling and dosing times as recorded in CRF will be used for analysis. From the plasma concentration-time data, the following pharmacokinetic parameters from the oral phase will be determined, as data permit: AUC(0-t), C_{max}, t_{max}, Day 1 C₂₄, and C_τ. From the plasma concentration-time data, the following pharmacokinetic parameters from the injection phase will be determined, as data permit: AUC_{0-t}, C_τ, C_{max}, t_{max}, half-life (t_{1/2}), and absorption rate constant (K_A).

Plasma CAB concentration data will be presented in graphical and/or tabular form and will be descriptively summarized by treatment and cohort.

Population PK analyses using non-linear mixed effects modelling software NONMEM (ICON; Hanover, MD) may be done with the data from the study in conjunction with previous data to inform dose/dosage regimen for CAB 400 mg/mL formulation in Part 1 (Cohorts 4 and 4b) and Part 2 of the study.

Details of PK analyses and simulations will be provided in the report and analysis plan (RAP) separately.

10. STATISTICAL CONSIDERATIONS

10.1. Statistical Hypotheses

This study is primarily designed to describe the PK profile of CAB 400 mg/mL injection administered in different routes. No formal hypothesis will be tested.

10.2. Sample Size Determination

In Part 1, 80 participants in Cohorts 1-4 will be randomly assigned study intervention (CAB 400 mg/mL or AC CAB 200 mg/mL), 24 participants in Cohort 4b will receive study intervention with CAB 400 mg/mL, and approximately 20 participants in Cohort 4h will be randomly assigned study intervention rHuPH20 with CAB 400 mg/mL or CAB 200 mg/mL, such that approximately 93 evaluable participants will be receiving CAB (15 in each of Cohorts 1-4 and Cohort 4h, 18 in Cohort 4b). In Part 2, 22-44 participants will be enrolled to Cohort 5 and 6 (if conducted) and randomly assigned study intervention (CAB 400 mg/mL or AC CAB 200 mg/mL) such that approximately 16 evaluable participants receiving CAB from each cohort complete the study.

With the determined sample size, certain statistical precision can be achieved when estimating PK trough concentrations using sample geometric mean trough concentration as shown below in [Table 3](#):

Table 3 Statistical Precision When Estimating PK Trough Concentration

Exp. Arm	Time Point	Assumptions*			Precision+ when estimating trough Concentration 90%CI	
		Mean (LgConc.)	SD (LgConc.)	True Geo. Mean (To be observed)		
Cohorts 1-4: 600 mg - >400 mg Q4W (N=15)	Week 4	0.3291	0.66079	1.3898	1.0290	1.8769
	Week 8	0.6123	0.47376	1.8446	1.4871	2.2881
Cohort 4h: 400 mg Q4W (N=8)	Week 4	0.3292	0.66079	1.3898	0.8927	2.1636
Cohorts 5/6: 1200 mg Q3M (N=16)	Week 12	0.0311	0.59603	1.0316	0.7944	1.3395
	Week 24	-1.3837	1.11507	0.2507	0.1538	0.4086

*Assumptions for Q4W arm were from pooled PK Trough data from FLAIR (Study 201584) and ATLAS (Study 201585) i.e. 1.44 µg /mL; assumptions for Q3M were from simulated PK Trough data from a single 1200 mg dose in 80% male and 20% female.

+Precisions were calculated based on t-distribution.

In addition, the bioavailability of CAB 400 mg/mL formulation administered IM to *gluteus medius* will be assessed relative to IM administration to lateral thigh or SC administration to abdomen from Q4W cohorts of Part 1. Additionally, C_τ following

CAB 400 mg/mL formulation administration in Part 1 will be compared to historical PK data of CAB 200 mg/mL using cross-study comparisons.

Table 4 Statistical Precision When Estimating Ratio of PK Trough Concentration

Exp. Arm	Time Point	Assumptions*			Precision* for estimating Ratio of Trough Concentration		
		CVb%	SD (LgConc.)	Ratio of Geo. Mean Concentration (To be observed)	Half Width of (Δ Lg Conc).	90% CI for Ratio	
Cohorts 1-4: CAB 400 mg/ml (N=15)/ Historical CAB 200 mg/ml (N=579)	Week 4	74%	0.66079	0.7	0.28470	0.5266	0.9306
				0.8		0.6018	1.0635
				0.9		0.6770	1.1964
				1.0		0.7522	1.3294
				1.1		0.8275	1.4623
				1.2		0.9027	1.5952
				1.3		0.9779	1.7282
Cohort 4h: CAB 400 mg (N=8)/ Historical CAB 200 mg/ml (N=579)	Week 4	74%	0.66079	0.7	0.387538	0.4751	1.0313
				0.8		0.5430	1.1787
				0.9		0.6109	1.326
				1.0		0.6787	1.4733
				1.1		0.7466	1.6207
				1.2		0.8145	1.768
				1.3		0.8823	1.9154
Cohorts 1-4: CAB 400 mg/ml (N=15) / Historical CAB 200 mg/ml (N=577)	Week 8	50%	0.47376	0.7	0.20413	0.5707	0.8585
				0.8		0.6523	0.9812
				0.9		0.7338	1.1038
				1.0		0.8154	1.2265
				1.1		0.8969	1.3491
				1.2		0.9784	1.4717
				1.3		1.0600	1.5944

* CVb%, SD (Lg Conc) is from pooled Cabotegravir trough concentration data from ATLAS and FLAIR studies

+Precisions were calculated based on t-distribution.

CCI

CCI

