2. SUMMARY OF KEY PROTOCOL INFORMATION

2.1. Changes to the Protocol Defined Statistical Analysis Plan

There were no changes or deviations to the originally planned statistical analysis specified through protocol amendment 6.

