8.1.5.1. Statistical Methodology Specification

The following PK statistical analyses will only be performed if sufficient data is available (i.e., if participants have well defined plasma profiles).

Endpoint / Variables

 AUC(0-τ), C_{max}, and C_{τ} for CAB 400 mg/mL following CAB IM (gluteus medius or vastus lateralis) or SC dosing
Model Specification for Pairwise and Historical Comparisons

 Pairwise comparisons between cohorts receiving the same dose of CAB400 but via different administration routes of CAB 400 mg/mL geometric mean plasma C_{τ}, C_{max}, and plasma AUC(0-τ) for Cohorts 1, 2, 3, 4, 4b and 4h will be conducted, as specified in Section 5.1. Cross study comparisons of geometric mean plasma C_{τ} for Cohorts 1, 2, 3, 4, 4b and 4h, and Cohort 5 compared to historical CAB 200 mg/mL data will be conducted, as specified in Section 5.1. Following log transformation, PK parameters will be separately analyzed using a linear regression model with a fixed effect term for treatment, with allowance for unequal variances for each treatment group (using the repeated / group=treatment option in the MIXED procedure to model unequal variances and DDFM=KENWARDROGER option for adjusted degrees of freedom). Point estimates and corresponding 90% CIs will be constructed for the treatment differences. Point estimates and their 90% CIs will then be transformed back to provide point estimates and 90% CIs on the original scale.
Historical CAB 200 mg/mL Data

 Anonymized reference dataset(s) containing the historical PK data from the ATLAS [201585], FLAIR [201584], and ÉCLAIR [201120] studies will be used in the historical cross-study comparison analyses described above. For ATLAS and FLAIR, concentrations meeting the definition of 'evaluable' as defined in the study-specific RAPs (e.g., excluding samples collected outside the ± 4 days evaluable sample window) will be used.
Model Checking & Diagnostics

 Model assumptions will be applied, but appropriate adjustments may be made based on the data.
Model Results Presentation

 Statistical analysis by analysis of variance (ANOVA) will be presented in tabular format with geometric mean ratios and corresponding 90% CI for the comparisons mentioned above.

Endpoint / Variables

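### Protocol Table 4 states precision from a pooled-variance t interval, but the SAP analyses the same historical comparisons with unequal variances, so the stated widths are too narrow at the stated N, most of all for Cohort 4h

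*Protocol*

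**What the plan says.** **Table 4 (Protocol 10.2)** shows 90% intervals for the ratio of trough concentrations against pooled ATLAS/FLAIR data. Rows include "Cohorts 1-4: CAB 400 mg/ml (N=15)/ Historical CAB 200 mg/ml (N=579" and "Cohort 4h: CAB 400 mg (N=8)/ Historical CAB 200 mg/ml (N=579", with log half-widths of 0.28470 and 0.387538. The Week 8 row (15 against 577) has 0.20413. One SD per time point is given (0.66079 at Week 4, 0.47376 at Week 8), taken from the historical studies. The footnote says only this: "Precisions were calculated based on t-distribution". It does not give the degrees of freedom.

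**Analysis.** Protocol 10.4.2 plans a linear regression on the log scale with a treatment term and is silent on the variance structure. SAP 8.1.5.1 fits the model "with a fixed effect term for treatment, with allowance for unequal variances for each treatment group", with Kenward-Roger degrees of freedom. SAP 2.1 states: "There were no changes or deviations to the originally planned statistical analysis specified through protocol amendment 6".

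**Table 3 (Protocol 10.2).** The row "Cohort 4h: 400 mg Q4W (N=8" has a geometric mean of 1.3898, the same as the Week 4 value of the Cohorts 1-4 row, whose first dose is 600 mg. The Cohorts 5/6 rows are labelled as a three-monthly 1200 mg regimen, but the footnote says "assumptions for Q3M were from simulated PK Trough data from a single 1200 mg dose in 80% male and 20% female".

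**The concern.** No hypothesis is tested (Protocol 10.1, SAP 2.4), so these precision tables carry the visible justification for cohort size. Table 4 compares 8 or 15 new participants with almost 580 historical ones. Under a common variance, the historical data fix the SD almost exactly and the t quantile is close to normal. Under group-specific variances, the small cohort must estimate its own SD, and its few degrees of freedom govern the interval. Table 4 therefore describes a different interval from the one that will be reported, and it is most optimistic for the smallest cohort. In Table 3, a reader planning around the expected level of the trough would be misled by two centres that do not match their row labels.

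**Working it through.** **Inputs (Protocol 10.2).** Two-sided 90% intervals. Week 4: SD 0.66079, N = 15 or 8 against 579. Week 8: SD 0.47376, N = 15 against 577.

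**Step 1: reproduce Table 4.** Pooled formula: half-width = t(0.95, n1+n2−2) × SD × √(1/n1 + 1/n2).

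- 15 v 579: 1.64743 × 0.17281 = 0.28469 (stated 0.28470)
- 8 v 579: 1.64746 × 0.23523 = 0.38754 (stated 0.387538)
- 15 v 577: 1.64744 × 0.12390 = 0.20412 (stated 0.20413)

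A normal quantile gives 0.28425, 0.38692 and 0.20380. A one-sample t on the new cohort gives 0.30051, 0.44262 and 0.21545. Neither matches.

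**Step 2: the SAP model at the same inputs.** For a two-group contrast with a variance per group, the degrees of freedom are (a+b)² / [a²/(n1−1) + b²/(n2−1)], where a = SD²/n1 and b = SD²/n2. The standard error is unchanged when both SDs equal the planning value. Only the t quantile moves.

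| Row | df | t | Half-width | Change | SAP-model interval at ratio 1.0 | Table 4 |
|---|---|---|---|---|---|---|
| Cohorts 1-4, Week 4 (15) | 14.7 | 1.7551 | 0.3033 | +6.5% | 0.738–1.354 | 0.7522–1.3294 |
| Cohort 4h, Week 4 (8) | 7.2 | 1.8869 | 0.4439 | +14.5% | 0.642–1.559 | 0.6787–1.4733 |
| Cohorts 1-4, Week 8 (15) | 14.7 | 1.7551 | 0.2175 | +6.5% | 0.805–1.243 | 0.8154–1.2265 |

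Protocol 10.2 counts 15 evaluable in Cohort 4h across two arms, so one arm may have 7. Then df = 6.1, the half-width is 0.4862 and the interval is 0.61–1.63.

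**Step 3: N needed for the stated widths under the SAP model.**

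- Cohorts 1-4, Week 4 (stated 0.2847): N = 16 gives 0.2926, N = 17 gives 0.2829.
- Cohorts 1-4, Week 8 (stated 0.2041): N = 16 gives 0.2098, N = 17 gives 0.2028.
- Cohort 4h (stated 0.3875): N = 9 gives 0.4111, N = 10 gives 0.3849.

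**Step 4: sensitivity to the new cohort's SD.** If it is 0.8 to 1.2 times the historical SD, the half-width is 0.86 to 1.27 times the stated value (N = 15) and 0.92 to 1.37 times (N = 8). Averaged by simulation over sampling variation in both SDs, with the true SD at its planning value, the half-width is 0.298 (about +4.6%) for N = 15 and 0.428 (about +10.6%) for N = 8.

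**Step 5: Table 3.** The printed intervals reproduce with n−1 df. For Cohort 4h, the half-width is 1.8946 × 0.66079/√8 = 0.4426, and 1.3898 × exp(±0.4426) = 0.893 to 2.164. The input is the issue. Under assumed dose proportionality:

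- nominal 400 mg: 1.3898 × 400/600 = 0.93 (0.60–1.44)
- 427.6 mg, the amount that Protocol 6.1.3 states will be administered: 1.3898 × 427.6/600 = 0.99 (0.64–1.54)

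The log half-width is 0.4426 in every case. The Week 24 centre of 0.2507 comes from simulation of one 1200 mg dose, so it is not a trough after a second injection.

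**The case against.** - **Full enrolment recovers the stated widths.** This is true: 18 active participants per cohort and 10 per Cohort 4h arm are planned, and Step 3 reaches the stated widths at 17 and 10. But Table 4 labels its rows N=15 and N=8, the evaluable numbers on which the plan relies, and Cohort 4h would need every participant evaluable.
- **The widening is not certain.** This stands. It holds at the planning SD in both groups, and an observed SD that is lower in the new cohort could give a narrower interval than stated.
- **SAP 2.1 may be accurate.** Protocol 10.4.2 names no variance structure, and Protocol 10.4 leaves technical detail to the analysis plan. The SAP can fairly be read as supplying that detail. A reader might infer an undeclared deviation, but the documents do not establish one.
- **Little depends on it.** No hypothesis or threshold is tied to these intervals, and for Cohorts 1-4 the shift is small.
- **The Table 3 centres are declared assumptions.** The source is footnoted, and rescaling does not change log-scale precision. Proportionality across route, formulation and rHuPH20 co-administration is itself an assumption. What remains is the mismatch between label and input.

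**Conclusion.** The mismatch is real and modest. At the stated N, with the planning SD in both groups, the SAP's intervals are 14.5% wider on the log scale than Table 4 shows for Cohort 4h and 6.5% wider for Cohorts 1-4.

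Four stronger readings are not supported:

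- Table 4 contains no arithmetic error. It is correct for the common-variance interval that it uses.
- The percentages are not a forecast of the observed widths, which depend on each new cohort's own SD.
- The two tables cannot be called the only sample-size justification, because Protocol 10.2.1 covers Cohort 4b and its content is withheld from the public text.
- The Week 24 row should not be replaced by 1.0316 + 0.2507 = 1.28. A sum of geometric means is not the geometric mean of a sum, and the answer depends on a within-person correlation that the documents do not give. The row is also moot: SAP 2.3 records that Cohort 5 receives no second injection and that Cohort 6 was not needed.

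**What to change.** 1. Restate Table 4 with the unequal-variance intervals from Step 2, and give the degrees of freedom. Add that the actual width depends on the new cohort's SD, and that the present figures would need about 17 evaluable per cohort and 10 per Cohort 4h arm. Show the 7-evaluable case for Cohort 4h.
2. Keep the SAP's unequal-variance model. The historical data come from people with HIV given another formulation, so a common variance cannot be taken for granted. Add a sentence to SAP 2.1 naming the variance model and saying that Table 4 assumed a common variance.
3. In Table 3, either state that the Cohort 4h centre is the unscaled 600 mg value, or scale it under an explicit dose-proportionality assumption and say which of the two documented amounts is used.
4. Delete the Cohorts 5/6 Week 24 row, or label it as a single-dose value.

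The cost is a few corrected figures, slightly less favourable than those printed, and one added sentence in the SAP. Enrolment and the planned analysis do not change.
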